A pilot project to investigate
the use of an external
vestibular prosthesis potential
to improve clinical
management of Chronic
Subjective Dizziness (CSD)

NCT# 02048670

July 22, 2013

IRB Minimal Risk Protocol Template

General Study Information

Principal Investigator: [name].

Study Title: A pilot project to investigate the use of an external vestibular prosthesis potential to improve clinical management of Chronic Subjective Dizziness (CSD)

Protocol version number and date: 01, 22 JUL 2013

Purpose

Hypothesis: #1 The use of the BalanceBelt™ will provide differential information about body sway movements during specific clinical balance and gait tasks in patients with CSD that is not currently available through routine measures.

Hypothesis: #2 The use of the BalanceBelt™ will provide for a more rapid rate of reduction in patient symptoms compared to the historical data from the traditional habituation therapy method.

Aims, purpose, or objectives: #1 Motion detectors contained in the BalanceBelt™ will be used to record information about the subtle changes in posture and gait that are thought to occur in patients with CSD with the tractors turned off. The goal of this portion of the study will be to improve diagnostic strategies for CSD.

Aims, purpose, or objectives: #2 In this second portion of the study we will test the benefits of a 1-week intensive rehabilitation program using the BalanceBelt™ with tractors activated in 10 patients with CSD. The goal of this study will be to develop a treatment that is quicker and more effective than current therapies.

Background (*Include relevant experience, gaps in current knowledge, preliminary data, etc.*):

Chronic subjective dizziness (CSD) is the second most common condition identified in patients referred to Mayo Clinic for persistent dizziness. We manage nearly 500 patients with CSD each year. CSD is a syndrome of persistent non-vertiginous dizziness and unsteadiness that may be worsened by patients' own motion, exposure challenging visual stimuli such as busy shopping areas, or performance of precision visual tasks such as reading. CSD develops in about 25% of patients following medical events that acutely disrupt balance. Once established, CSD may last for many years, even if the problems that triggered it resolves. As a result, CSD causes considerable distress and functional impairment, even to the extent of work disability and disruption of family and social life (Staab, 2012).

Over the last decade, the Mayo Clinic Integrated Neurotology team, and other investigators around the world have developed two treatment strategies for CSD. One uses serotonergic medications such as sertraline (Zoloft) and venlafaxine (Effexor). The other is a variation of vestibular and balance exercises known as vestibular habituation. These therapies reduce symptoms for 60-80% of patients when administered by experts in the field

(Staab, 2012). However, they have important shortcomings. They are time-consuming, taking a minimum of 2-3 months of diligent treatment to achieve best results. They usually achieve a partial reduction in symptoms, which improves patients' functioning, but falls short of a cure. They can make patients worse, rather than better, when used by clinicians who are unfamiliar with them.

A new theory about altered postural control mechanisms in CSD suggests that it could be diagnosed more accurately and treated more quickly by using an external vestibular prosthesis to enhance sensory feedback during vestibular exercises. A suitable prosthesis is the BalanceBelt™, which is currently in final beta testing by BalanceTek, the company that developed it. This device has been shown to have efficacy in reducing sway behavior in patients that have bilateral vestibular hypofunction (Sienko et al, 2010). For those patients with deficient vestibular systems the belt provides information that is missing from the lack of vestibular system cues for detecting sway or leaning behavior, hence drawing attention to the information that is missing. The BalanceBelt™ is a comfortable, self-contained unit worn under the clothes around the waist. It has sensitive motion detectors and small tactors that vibrate against the skin at four locations to provide information about posture and motion. Patients with CSD do not have permanent vestibular deficits, but underutilize vestibular signals because they develop visual or somatosensory dependence. We expect the BalanceBelt™ to reset this error by providing patients with reliable motion stimuli.

We propose two preliminary studies using the BalanceBelt™ in patients with CSD. In the first study, we will use the motion detectors contained in the BalanceBelt™ to record information about the subtle changes in posture and gait that are thought to occur in patients with CSD. This goal of this study will be to improve diagnostic strategies for CSD. We will compare postural movements recorded with BalanceBelt™ with tactors turned off during quiet stance, normal walking (Dynamic Gait Index), functional reach test, and the Sensory Organization Test in 10 patients with CSD and 10 age and gender matched normal individuals. In the second study, we will test the benefits of a 1-week intensive rehabilitation program using the BalanceBelt™ with tactors activated in 10 patients with CSD. The goal of this study will be to develop a treatment that is quicker and more effective than current therapies.

References:

Staab, J.P: Chronic subjective dizziness. *Continuum Lifelong Learning Neurol* 2012; 18(5):1118–1141.

Subject Information – charts, records, images, or specimens are considered 'subjects'

Target accrual: *Proposed number of subjects to be included in your study at your site. "Subjects" may include Mayo Clinic charts, records, or specimens, and/or charts, records, or specimens received at Mayo Clinic from external sources for collaborating analysis by the investigator under this IRB application:*

Subject population: 20 patients with diagnosis of Chronic Subjective Dizziness (CSD) and 10 normal volunteers.

- Inclusion Criteria:
1. Subjects will be 25-70 years of age inclusive and pregnant women may participate.
 2. Patients will have CSD as their primary diagnosis for the cause of their balance and dizziness complaints provided by the Behavioral Medicine Program for Dizziness, a division of the Department of Psychiatry & Psychology.
 3. Normal volunteers will have a negative history of otologic & neurologic disorders and no history of dizziness and balance problems.
 4. Normal volunteers will have normal findings on a screening office examination for peripheral and central vestibular system involvement (see methods for details of the examination) and screening for normal or symmetrical hearing loss of explainable origin.

- Exclusion Criteria:
1. Patients with positive indications from testing of peripheral and/or central vestibular system involvement that is felt to be influencing the symptoms reported beyond the CSD alone.
 2. Patients with mobility restriction that would prevent participating in the tests or the intensive therapy trials.
 3. Subjects with hearing impairment that interferes with oral communication.

Will a Certificate of Confidentiality be obtained? *If yes, provide an explanation.*

NO

Study Design

Methods: *Describe, in detail, the research activities that will be conducted under this protocol:*

For Hypothesis and aim #1: Ten consecutive patients, ages 25-70 years, diagnosed with CSD after completion of their routine evaluation in the Dizziness and Balance disorders laboratory and their evaluation by the Behavioral Medicine program for dizziness, would then be recruited for participation in the study. If they agree to participate they will individually be placed through the following evaluations while wearing the BalanceBelt™ with the tractors turned off but the recording elements turned on. Each of these tests is a standard evaluation tool used in the Vestibular and Balance Laboratory on a routine basis:

1. Dynamic Gait Index – evaluates gait under normal walking and under conditions of head turns, walking around two objects on the floor, stepping over a shoe box, walking at different speeds, walking with a stop and 180 degree turn, walking up and down 3 standard steps with hand rails. During the evaluation the physical therapist or the audiologist guards the subjects at all times walking with the subject and the subject wears the harness used for the test in #3 that has a hand grab to prevent falls.
2. Functional Reach Test – the subject stands in a stationary position and reaches out with a single arm as far as they can without taking a step. Here again the physical therapist or the audiologist is guarding the patient during the performance of the test, again with the subject in the harness used in #3 with the hand grab to prevent falls.

3. Sensory Organization Test – this is a 6 condition standard evaluation of balance control performed on a dynamic platform that can record sway movement in the A/P dimension while the sensory inputs from proprioception and vision are varied through the platform and visual surround movements. The subject wears a full chest harness that is fastened to a roll bar above the subject to prevent any falls.

For each of the patients an age and gender matched normal (± 5 years) volunteer will go through the same evaluations. The time for testing will take 45 minutes. Normal subjects will be recruited through written advertisements from visitors and / or accompanying persons for patients to Mayo Clinic. Each of the normal subjects will go through an office vestibular examination that will consist of direct monitoring for nystagmus in all positions of gaze with and without visual fixation present. They will also undergo the head thrust test with visual fixation present and headshake test with visual fixation absent. Pursuit and saccade office examination will be performed with a hearing screening by pure tones only. If any abnormalities are revealed with the screening the normal volunteer will be advised as to formal testing that should be performed via their primary care physician also being notified.

For Hypothesis and aim #2: Ten consecutive patients, ages 25-70 years, diagnosed with CSD who live within a 30 minute drive time of the Rochester Mayo campus will be asked to participate in the habituation therapy activities typically used as treatment of CSD but with an intensive treatment program using the exercises at home for the week. The patients will be using the BalanceBelt™ with the tractors activated. The typical therapy evaluations pre-therapy will be taken in addition to Visual Analog Scales related to the intensity of symptoms provoked by visual motion, head movements and walking in visually complex environments. These same measures will be taken at the end of the week of intensive therapy at a return visit to check their exercise activities prior to continuing their progressive home treatment. The one week of intensive therapy will be performed prior to starting any recommended medications or medication changes for the CSD. The therapy will be conducted by one of the Physical Therapists certified in Vestibular and Balance therapy.

Following the intensive therapy the patient will continue with the therapy activities and medication trials as is standard currently for the CSD patients.

Resources: *Describe the available resources to conduct the research (personnel, time, facilities, mentor commitment, etc.):*

All of the equipment and procedures described above are already in place and used routinely by the Audiologists and Physical therapists that work in the Dizziness and Balance Disorders Center on Gonda-12 in the department of Otolaryngology. The only acquisition is that of the BalanceBelt™ for which the department of Otolaryngology research committee has approved a request for \$7800 from the small grants program to cover the cost of the belt (\$6000) and the 30% indirect costs (\$1800).

Check all that apply. If none apply, leave blank:

The research involves contact or interaction with subjects, for example, surveys, questionnaires, observation, blood draw.

Blood Collection

If this study involves prospective blood collection by finger, heel, ear stick or venipuncture, complete the following:

From healthy, non pregnant, adult subjects who weigh at least 110 pounds. For a minimal risk application, the amount of blood drawn from these subjects may not exceed 550ml in an 8 week period and collection may not occur more frequently than 2 times per week.

Volume per blood draw: _____ ml

Frequency of blood draw (e.g. single draw, time(s) per week, per year, etc.) _____

From other adults and children considering age, weight, and health of subject. For a minimal risk application, the amount of blood drawn from these subjects may not exceed the lesser of 50 ml or 3 ml per kg in an 8 week period, and collection may not occur more frequently than 2 times per week.

Volume per blood draw: _____ ml

Frequency of blood draw (e.g. single draw, time(s) per week, per year, etc.) _____

Review of Chart, Images, Specimens

Provide the date range for collection of data and/or specimens that will be included in your research dataset.
(*Example: 01/01/2000 to 12/31/2012*)

Date range: From _02/01_/2014 to 01/_31/2015

Check all that apply:

This study involves only data and/or specimens that will be collected after submission to the IRB.

Data Confidentiality, HIPAA Subject Identifiers

Review the list of subject identifiers below and, if applicable, check the box next to each subject identifier being recorded at the time you are collecting/abstracting data/specimens for use in this study.

Subject Identifiers: Individually identifiable information, including demographic data, that identifies the individual or for which there is reasonable basis to believe it can be used to identify the individual. NOTE: Identifiers apply to subjects enrolled in your study and to the subject’s relatives, household members, employers, etc.

Internal refers to subject identifiers that will be included in the dataset maintained by the study team.

External refers to subject identifiers that will be shared with persons outside of the immediate study team, for example, sent to an external collaborator or shared with a national registry.

SUBJECT IDENTIFIERS Check all that apply	INTERNAL IDENTIFIER	EXTERNAL IDENTIFIER
Name		
Social Security number		
Medical record/patient registration number, lab accession, specimen or radiologic image number	x	
Study number, subject ID, or any other unique identifying number, characteristic or code that can be used to link the identity of the subject to the data	x	
Dates: All elements of dates [month, day, and year] directly related to an individual. Their birth date, date of death, date of diagnosis, etc. Note: Recording a year only is not a unique identifier.	x	
Medical device identifiers and serial numbers		
Biometric identifiers, including finger and voice prints, full face photographic images and any comparable images		
Web Universal Resource Locators (URLs), Internet Protocol (IP) address numbers, email address		
Street address, city, county, precinct, zip code, and their equivalent geocodes		
Phone or fax numbers		
Account, member, certificate or professional license numbers, health beneficiary numbers		
Vehicle identifiers and serial numbers, including license plate numbers		
If None of the above identifiers will be recorded or maintained in the dataset and/or sent outside of the study team, please check “None”.		

Statistical Information

Note: Power analyses and study endpoints are not needed for a pilot or feasibility studies.

No statistical information. *If checked, please explain:*

Statistical Considerations

Power Statement: Power analyses not used as this is a pilot study.

Data Analysis Plan:

For Hypothesis and aim #1: The outcome parameters from the BalanceBelt™ that represent the total amount of sway and sway activity in the A/P and M/L directions will be compare between the CSD patients and the normal age matched volunteers via the Wilcoxon rank-sum test for mean comparisons.

For Hypothesis and aim #2: The visual analog scale scores pre & post the week of intensive therapy will be compared for the 10 subjects using also the Wilcoxon test for mean comparisons.

Endpoints

As this is a pilot study no fixed endpoints will be used.

Primary:

Secondary:

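### Hypothesis #2 credits the belt with faster improvement than historical therapy, but the uncontrolled one-week pre/post test in ten patients can show neither the belt's part nor the faster rate.

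*Combined protocol and SAP*

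**What the plan says.** All references are to the combined protocol and SAP.

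- **Purpose, Hypothesis #2** reads as follows: "The use of the BalanceBelt™ will provide for a more rapid rate of reduction in patient symptoms compared to the historical data". Those earlier data concern conventional habituation treatment. The subject of the claim is the belt. Aim #2, directly below, is worded differently: it tests an intensive rehabilitation week that uses the belt.
- **Background:** the rationale is specific to the belt, which is expected to correct patients' underuse of vestibular signals. On existing treatment (serotonergic medication and habituation, described together) it says: "These therapies reduce symptoms for 60-80% of patients when administered by experts in the field", and "They are time-consuming, taking a minimum of 2-3 months of diligent treatment to achieve best results".
- **Study Design, Methods, aim #2:** ten consecutive patients do the "habituation therapy activities typically used as treatment of CSD but with an intensive treatment program using the exercises at home for the week". In the same paragraph: "The patients will be using the BalanceBelt™ with the tractors activated". Measures are taken before therapy and at the end of the week. On drug treatment: "The one week of intensive therapy will be performed prior to starting any recommended medications or medication changes for the CSD".
- **Data Analysis Plan, aim #2:** "The visual analog scale scores pre & post the week of intensive therapy will be compared for the 10 subjects", by a Wilcoxon test. No other Aim 2 analysis is given.
- **Review of Chart, Images, Specimens:** "Date range: From _02/01_/2014 to 01/_31/2015".

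**The concern.** Hypothesis #2 makes two claims: that the belt causes the improvement, and that the improvement comes faster than it did historically. The planned analysis addresses neither.

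A significant one-week fall in VAS would be the only test result available for this hypothesis, and the hypothesis as worded invites the reader to take it as the belt speeding recovery. The same fall could occur with a belt that does nothing, and the plan holds no rate for traditional therapy to set beside it. Aim #2's stated goal is to develop a quicker and more effective treatment, so a misattributed pilot result could misdirect the next study.

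**Working it through.** The plan states no power, alpha, effect size, VAS mean or SD, so it has no figure of its own to reproduce. The check is first a comparison of the hypothesis with the plan, then an illustration under stated assumptions.

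**1. What the hypothesis needs and what the plan supplies**

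| Needed for Hypothesis #2 | Supplied for Aim 2 |
|---|---|
| Patients with the intensive programme but no active belt | 0 of 10 |
| Patients with the active belt but no intensive programme | 0 of 10 |
| Concurrent controls | 0 |
| Historical data set, outcome and time point | None named |
| Planned analyses using historical data | 0 |
| Null hypothesis: change equals the historical rate | Null tested: change equals zero |

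Belt and intensity change together in all ten patients, so their effects cannot be separated. Holding medication starts and changes until after the week removes one rival explanation. Exercise intensity, time, regression to the mean and expectation remain.

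The Background figures cannot serve as the benchmark. They cover medication and habituation together. One is a proportion of patients with reduced symptoms, the other a time to best results, and neither is a one-week VAS change. If a historical comparison were added, it would still mix belt with intensity, assuming (as the Methods imply) that traditional therapy was less intensive and used no belt.

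**2. How often the planned test is significant when the belt does nothing**

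Assumptions, none of them document figures: the Wilcoxon test is the paired signed-rank version; alpha is 0.05 two-sided; within-patient improvements are normal with SD 1 and mean *d*; and all of *d* comes from causes other than the belt.

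*Cut-off.* With n = 10 there are 2^10 = 1,024 equally likely sign patterns under the null. The smaller rank sum W gives

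- W ≤ 8: 25 patterns in each tail, two-sided p = 2 × 25/1,024 = 0.0488;
- W ≤ 9: 33 patterns in each tail, two-sided p = 2 × 33/1,024 = 0.0645.

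The test therefore rejects at W ≤ 8. With no change at all, the chance of significance in the direction of improvement is 25/1,024 = 2.4%.

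*Simulation.* 400,000 ten-patient studies for each *d*:

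| Non-belt improvement *d* (SD of change) | Studies with significant improvement |
|---|---|
| 0 | 2.4% |
| 0.3 | 12.9% |
| 0.5 | 28.2% |
| 0.8 | 59.7% |
| 1.0 | 78.5% |

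A separate run of 100,000 studies for each *d*, counting rejections in either direction, gave 13.2%, 28.3%, 59.9% and 78.5% for *d* = 0.3 to 1.0.

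**3. Whether a control arm of pilot size would settle it**

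For a belt versus no-belt comparison with the same programme in both arms, 80% power and two-sided alpha 0.05, the normal-approximation formula is n per arm = 2(1.96 + 0.84)²/d². At an assumed difference of 0.5 SD this is 2 × 7.85/0.25 = 62.8, so 63 per arm. With 10 per arm the power is Φ(0.5 × √5 − 1.96) = Φ(−0.84) = 20%. Such an arm would give an estimate, not a confirmatory test, so the remedy below does not ask for one.

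**The case against.** The best reply is that this is a declared pilot without fixed endpoints. A hypothesis states an expectation, and nothing in the plan says that a significant VAS change will be credited to the belt alone. Aim #2 names the combined programme, so Hypothesis #2 can be read as programme-with-belt against the usual method. That reading softens the attribution problem. It does not supply the historical comparison, which the hypothesis names and the analysis plan omits. Pilot status explains the absence of power and endpoints, but not a comparative claim with no comparison behind it.

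Other points on that side:

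- **Routine therapy evaluations** are also taken before and after the week and might link to historical records. This is true, but no analysis of them is planned.
- **The data window** fills a template field for the research dataset, and a published benchmark could lie outside it. Agreed: the window alone does not show that no benchmark was intended. The finding rests on none being specified.
- **Spontaneous recovery in one week** is unlikely in a condition described as persistent and lasting for years. That weakens time as an explanation, but leaves intensity, expectation and regression to the mean.
- **The simulated percentages** would be the same for any uncontrolled study of ten patients. Correct; they illustrate the problem and are not evidence about this trial.
- **Aim #2 keeps a comparative goal.** It does, but as a purpose for developing a treatment, not as a result this study would test.

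**Conclusion.** The concern holds. Followed exactly, the plan cannot support Hypothesis #2: all ten Aim 2 patients get belt and intensified exercise together, none is a control, and no planned analysis uses historical data. This follows from the text alone and needs no numerical assumption.

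The illustrative size, about 13% to 79% of studies significant with a belt effect of zero, depends on the assumed range of 0.3 to 1.0 SD for non-belt improvement, normal changes, the paired test and two-sided alpha of 0.05. The pilot itself remains worthwhile as a description of change under the combined programme. The text should be corrected because the hypothesis claims more than the design can show.

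**What to change.** 1. **Purpose, Hypothesis #2.** Replace with: *Symptom scores will decrease over a one-week intensive habituation programme delivered with the BalanceBelt (tactors activated).*
2. **Historical comparison.** Remove it from the hypothesis. If it is kept, move it to the Aim 2 analysis, label it descriptive and hypothesis-generating, and name its data source, outcome and time point.
3. **Data Analysis Plan, aim #2.** Add: *The uncontrolled pre/post change is descriptive of patients receiving the combined programme; it cannot be attributed to the BalanceBelt, nor separated from exercise intensity, time, regression to the mean or expectation.*

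Aim #2 and the Aim 2 procedures need no change. The cost is two or three sentences of protocol text, with no added patients, visits, procedures or data. The price is a narrower claim: the statement of faster improvement than historical therapy is lost or becomes descriptive only.

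### Hypothesis #2 claims faster improvement than historical habituation therapy, but the plan neither supplies nor analyses any historical data

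*Combined protocol and SAP*

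**What the plan says.** - **Purpose, Hypothesis #2.** The claim is comparative: a "more rapid rate of reduction in patient symptoms compared to the historical data from the traditional habituation therapy method". The source, period and measure of those data are not given, nor whether they are patient records or summary results.
- **Review of Chart, Images, Specimens.** The form asks the applicant to "Provide the date range for collection of data and/or specimens that will be included in your research dataset". The typed answer is "Date range: From _02/01_/2014 to 01/_31/2015". Below it is the line "This study involves only data and/or specimens that will be collected after submission to the IRB", under an instruction to check what applies. No check mark is visible in the text available, so I give that line no weight.
- **Subject Information.** The form counts charts and records as subjects. The population entered is 20 patients with CSD and 10 normal volunteers.
- **Study Design, Methods, aim #2.** "The typical therapy evaluations pre-therapy will be taken in addition to Visual Analog Scales related to the intensity of symptoms". The same measures are repeated at the end of the week, before any recommended CSD medication is started or changed.
- **Data Analysis Plan, aim #2.** "The visual analog scale scores pre & post the week of intensive therapy will be compared for the 10 subjects", by a Wilcoxon test. No other analysis is given for this aim.
- **Background.** Of serotonergic medication and vestibular habituation together: "These therapies reduce symptoms for 60-80% of patients when administered by experts in the field". Best results are said to take at least 2-3 months.

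**The concern.** A claim that symptoms fall faster than under earlier therapy needs two rates: one from the belt patients and one from patients treated the earlier way. The plan collects the first and makes no provision for the second. If the ten belt patients improve over the week, the result could be reported as support for Hypothesis #2 although no comparison was made. The likely substitute is an informal contrast with the summary figures in the Background, which describe a different treatment mix over a much longer period.

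This is more than a missing test. Adding a comparison to the Data Analysis Plan would not be enough by itself, because neither the dataset nor the subject count includes historical records.

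**Working it through.** The plan states no sample-size figure, effect size or error rate, so there is nothing to reproduce. The check sets the sections side by side.

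1. **What the claim needs.** A rate of symptom change under traditional habituation therapy, on a measure also taken in the belt patients, over a comparable time.

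2. **Dataset window.** The window runs from 1 February 2014 to 31 January 2015, which is 365 days. The protocol is dated 22 July 2013. The window therefore opens 9 + 31 + 30 + 31 + 30 + 31 + 31 + 1 = 194 days later. Records of patients treated before the window are not part of the dataset as defined.

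3. **Accrual.** Aim #1 uses 10 patients with CSD and 10 matched normal volunteers. Aim #2 uses 10 patients with CSD. The sum is 10 + 10 + 10 = 30, and the form enters 20 + 10 = 30. Historical charts counted: 30 − 30 = 0.

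4. **Analysis.** Aim #2 has one planned comparison, post against pre within the same 10 patients. It contains no historical term or benchmark value.

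5. **Could the Background figures serve as the comparator?**
   - Treatment: they cover medication and habituation therapy together, whereas the belt week comes before any medication start or change.
   - Time: 2-3 months is about 2 × 365/12/7 = 8.7 to 3 × 365/12/7 = 13.0 weeks, against 1 week in aim #2.
   - Measure: they give a percentage improved and a duration. There is no VAS score, mean change or rate.
   - One-week value: none.

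   They cannot test a difference in rate.

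6. **What a comparison with records could show (illustration only).** For a difference in mean change between n₁ belt patients and n₂ historical patients, in units of a common standard deviation (SD), the 95% half-width is t(0.975; n₁ + n₂ − 2) × √(1/n₁ + 1/n₂). With n₁ = 10:
   - n₂ = 20: 2.05 × √0.150 = 0.79 SD
   - n₂ = 40: 2.01 × √0.125 = 0.71 SD
   - n₂ = 100: 1.98 × √0.110 = 0.66 SD

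   The values of n₂ are assumptions. The Background says the clinic manages nearly 500 patients with CSD a year, but that is before aim #2's limits are applied, and the document gives no count of usable records.

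**The case against.** The strongest reply is that there is no contradiction. The date range limits only what enters the study's own dataset. Hypothesis #2 does not say that the historical data are patient charts, and published or previously summarised results could be used without any record entering the window. That stands. A reader might infer that the plan's own window shuts out the comparator; this is too strong, because it follows only if patient-level records are meant. A reader might also take the prospective-only line as a second proof. It is an option on a check list with no visible mark, so it is not one.

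A reader might further try to size the problem by testing the number improved out of ten against 60% or 80%. The documents do not support that either. Proportion improved is not a planned outcome, and the percentages do not describe habituation therapy alone.

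It is also fair to say that widening the window would achieve nothing by itself. Methods takes the VAS in addition to the typical evaluations, so historical VAS scores are not shown to exist. Nor is any one-week return visit in past patients.

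Pilot status does not answer the point. It explains the absence of a power calculation and of fixed endpoints. It does not supply a comparator for a hypothesis that is stated as a comparison.

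**Conclusion.** The concern holds in a limited form. Hypothesis #2 depends on historical data that the plan does not identify, collect, count or analyse, and the one benchmark in the document cannot stand in for them. The defect is the unidentified and unanalysed comparator; the date window is one sign of it and not the cause.

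Its size is that of a whole comparison: zero historical records, no planned contrast and no one-week reference value. Run as written, the trial can report a within-patient change over one week in 10 patients. It cannot support a conclusion that improvement is faster than with traditional therapy.

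This rests on the document naming no historical source elsewhere, and I found none. The half-width of about ±0.7 SD is illustrative. It assumes 40 comparable historical records, a common SD and roughly normal change scores.

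**What to change.** **Recommended.** Delete from Hypothesis #2 the clause that makes the comparison with historical data. The words claiming a more rapid rate would then have nothing to refer to, so reword the hypothesis as a reduction in symptom scores from before to after the week of intensive therapy with the belt active. Limit the conclusion to that within-patient change. The wish for a quicker treatment can remain in aim #2 as a development goal, but should not be reported as a finding. The cost is a narrower hypothesis, with no new patients, visits or data.

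**Alternative, only if suitable records exist.** First confirm that clinic records hold the same typical therapy evaluations at the start of habituation therapy and at a comparably early return visit, with dates. If the return visit came much later than one week, the mismatch in time scale remains. If the records qualify, make all of these changes together:
- Review of Chart, Images, Specimens: extend the date range back to a stated historical period and declare the use of existing data.
- Subject Information: count the historical charts in accrual.
- Data Analysis Plan: name the evaluations and add a belt-versus-historical contrast on them, with a confidence interval.
- Selection: apply aim #2's own limits to the charts, namely age 25-70, the same exclusions, the same drive-time limit, and no CSD medication start or change before the early return visit.

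The cost is a form amendment and chart abstraction. The number of eligible charts is unknown and should be established before choosing this route.
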